18.0 ADVERSE EVENTS

18.1 Adverse Event Characteristics

18.1.1 The AE collection/reporting period will begin with the first day of treatment with metformin and will be completed at 30days following treatment completion. AEs after study registration but prior to the first day of study treatment will be captured as ongoing concurrent secondary diagnoses and symptoms present at the start of study. AEs will be graded in accordance with the NCI Common Terminology Criteria for Adverse Events v4.0 (CTCAE) <http://ctep.cancer.gov/reporting/ctc.html>. If not described in the NCI-CTCAE, AEs will be graded according to their severity using the following criteria: grade 1 (mild), grade 2 (moderate), grade 3 (severe), and grade 4 (life threatening).

18.1.2 This is the attribution scale which will be utilized to attribute relatedness of toxicity to the study:

- Definite – The AE is clearly related to the study treatment.
- Probable – The AE is likely related to the study treatment.
- Possible – The AE may be related to the study treatment.
- Unlikely – The AE is doubtfully related to the study treatment.
- Unrelated – The AE is clearly NOT related to the study treatment.

18.1.3 A definition of expected adverse event and unexpected adverse event:

18.1.3.1 Expected adverse events are those that have been previously identified as resulting from administration of the agent. For purposes of this study, an adverse event is considered expected when it appears in the current adverse event list in the Investigator's Brochure, the package insert, or is included in the informed consent document as a potential risk.

18.1.3.2 An adverse event is considered unexpected when it varies in nature, intensity, or frequency from information provided in

the current adverse event list in the Investigator's Brochure, the package insert or when it is not included in the informed consent document as a potential risk.

18.2 Adverse Event Reporting

- 18.2.1 All adverse events (all grades), regardless of perceived relationship to study treatment, will be reported and recorded on the appropriate CRFs. New AEs and SAEs that are ongoing at the end of the study will be followed for 30 days from the patient's receipt of the last dose of protocol therapy, unless they have resolved earlier. SAEs and drug related AEs ongoing at the end of study will be followed until resolution.
- 18.2.2 The AE description will include the nature of the experience, the date of onset, the resolution date, the severity of each sign or symptom reported using the NCI-CTCAE (version 4.0), the seriousness of the event, the potential relationship to study treatment, the course of action taken, and the outcome of the experience.
- 18.2.3 Serious adverse events are to be reported to the institutional review board (IRB) according to each board's reporting requirements and required time frame.
- 18.2.4 The Study Chair/Principal Investigator will be responsible for reporting all adverse events to the FDA as per their reporting requirements and time frame.
- 18.2.5 Any event that is reportable to the BCM IRB must also be reported to the DLDCCC Data Review Committee (DRC), via the Patient Safety Officer at [contact].

18.3 Safety Reporting Requirements for IND Holders

NA

18.4 Multicenter Guidelines

NA

19.0 Pregnancy

This study will exclude pregnant women. A subject who has a positive β hCG pregnancy test result at any time after the first dose of investigational therapy will be immediately withdrawn from participation in the study. All study conclusion/withdrawal assessments will be collected at the time of discontinuation as described in Section 9.0. Pregnancy information is to be recorded in the Case Report Forms. Pregnancy information will be collected from the first dose of investigational product to 30 days after the last dose. While pregnancy itself is not considered to be an SAE, it may result in an SAE. Any pregnancy complication or elective termination of a pregnancy for medical reasons will be recorded as an SAE and will be reported as such.

A spontaneous abortion is always considered an SAE and will be reported as such.

21.0 APPENDICES

APPENDIX A:

Staging criteria (AJCC Cancer Staging Manual 6th edition, 2002)

Oral Cavity

TX	Primary tumor cannot be assessed.
T0	There is no evidence of primary tumor.
Tis	Carcinoma is in situ.
T1	Tumor is 2 cm or less in greatest dimension.
T2	Tumor is more than 2 cm but not greater than 4 cm in greatest dimension.
T3	Tumor is more than 4 cm in greatest dimension.
T4 (lip)	Tumor invades through cortical bone, inferior alveolar nerve, floor of mouth, or skin of face—i.e., chin or nose.
T4a (oral cavity)	Tumor invades adjacent structures (e.g., through cavity) cortical bone, into deep [extrinsic] muscle of tongue [genioglossus, hypoglossus, palatoglossus, and styloglossus], maxillary sinus, skin of face).
T4b	Tumor invades masticator space, pterygoid plates, or skull base and/or encases the internal carotid artery.

Oropharynx

T1	Tumor is 2 cm or less in greatest dimension.
T2	Tumor is more than 2 cm but not more than 4 cm in greatest dimension.
T3	Tumor is more than 4 cm in greatest dimension.
T4a	Tumor invades the larynx, deep/extrinsic muscle of the tongue, medial pterygoid, hard palate, or mandible.
T4b	Tumor invades the lateral pterygoid muscle, pterygoid plates, lateral nasopharynx, or skull base or encases the carotid artery.

Larynx

Primary Tumor (T)

TX	Primary tumor cannot be assessed.
T0	There is no evidence of primary tumor.
Tis	Carcinoma is in situ.

Supraglottis

T1	Tumor is limited to one subsite of the supraglottis, with normal vocal cord mobility.
T2	Tumor invades mucosa of more than one adjacent subsite of the supraglottis or glottis or region outside the supraglottis (e.g., mucosa of base of tongue, vallecula, medial wall of pyriform sinus), without fixation of the larynx.

T3	Tumor is limited to the larynx with vocal cord fixation and/or invades any of the following: postcricoid area, pre-epiglottic tissues, paraglottic space, and/or minor thyroid cartilage erosion (e.g., inner cortex).
T4a	Tumor invades through the thyroid cartilage and/or invades tissues beyond the larynx (e.g., trachea, soft tissues of neck, including deep extrinsic muscle of the tongue, strap muscles, thyroid, or esophagus).
T4b	Tumor invades prevertebral space, encases the carotid artery, or invades mediastinal structures.
Glottis	
T1	Tumor is limited to the vocal cords(s) (may involve anterior or posterior commissure), with normal mobility.
T1a	Tumor is limited to one vocal cord.
T1b	Tumor involves both vocal cords.
T2	Tumor extends to the supraglottis and/or subglottis, and/or with impaired vocal cord mobility.
T3	Tumor is limited to the larynx with vocal cord fixation and/or invades paraglottic space, and or minor thyroid cartilage erosion (e.g., inner cortex).
T4a	Tumor invades through the thyroid cartilage and/or invades tissues beyond the larynx (e.g., trachea, soft tissues of the neck, including deep extrinsic muscle of the tongue, strap muscles, thyroid, or esophagus).
T4b	Tumor invades prevertebral space, encases the carotid artery, or invades mediastinal structures.
Subglottis	
T1	Tumor is limited to the subglottis.
T2	Tumor extends to the vocal cord(s), with normal or impaired mobility.
T3	Tumor is limited to the larynx, with vocal cord fixation.
T4a	Tumor invades cricoid or thyroid cartilage and/or invades tissues beyond the larynx (e.g., trachea, soft tissues of neck, including deep extrinsic muscles of the tongue, strap muscles, thyroid, or esophagus).
T4b	Tumor invades prevertebral space, encases the carotid artery, or invades mediastinal structures.
Hypopharynx	
T1	Tumor is limited to one subsite of the hypopharynx and 2 cm or less in greatest dimension.
T2	Tumor invades more than one subsite of the hypopharynx or an adjacent site, or measures more than 2 cm but not more than 4 cm in greatest dimension without fixation of the hemilarynx.

T3	Tumor is more than 4 cm in greatest dimension or with fixation of the hemilarynx.
T4a	Tumor invades thyroid/cricoid cartilage, hyoid bone, thyroid gland, esophagus, or central compartment soft tissue.
T4b	Tumor invades prevertebral fascia, encases the carotid artery, or involves mediastinal structures.

Neck Staging Under the TNM Staging System for Head and Neck Tumors (excluding nasopharynx and thyroid)

NX	Regional lymph nodes cannot be assessed.
N0	There is no regional nodes metastasis.
N1	Metastasis is in a single ipsilateral lymph node, 3 cm or less in greatest dimension.
N2	Metastasis is in a single ipsilateral lymph node, more than 3 cm but not more than 6 cm in greatest dimension; or metastasis is in multiple ipsilateral lymph nodes, none more than 6 cm in greatest dimension; or metastasis is in bilateral or contralateral lymph nodes, none greater than 6 cm in greatest dimension.
N2a	Metastasis is in a single ipsilateral lymph node, more than 3 cm but not more than 6 cm in greatest dimension.
N2b	Metastasis is in multiple ipsilateral lymph nodes, none more than 6 cm in greatest dimension.
N2c	Metastasis is in bilateral or contralateral lymph nodes, none more than 6 cm in greatest dimension.
N3	Metastasis is in a lymph node more than 6 cm in greatest dimension.

TNM Staging for the Larynx, Oropharynx, Hypopharynx, Oral Cavity, Salivary Glands, and Paranasal Sinuses

Stage Grouping

Stage 0	Tis N0 M0
Stage I	T1 N0 M0
Stage II	T2 N0 M0
Stage III	T3 N0 M0 T1 N1 M0 T2 N1 M0 T3 N1 M0
Stage IVA	T4a N0 M0 T4a N1 M0 T1 N2 M0 T2 N2 M0 T3 N2 M0 T4a N2 M0

Stage IVB T4b Any N M0
 Any T N3 M0
Stage IVC Any T Any N M1

Clinical Stage Grouping by T and N Status

	T1	T2	T3	T4a	T4b
N0	I	II	III	IVa	IVb
N1	III	III	III	IVa	IVb
N2	IVa	IVa	IVa	IVa	IVb
N3	IVb	IVb	IVb	IVb	IVb

APPENDIX B

Pregnancy testing guidelines and acceptable birth control methods

The safety of metformin in pregnant females has not been definitively established. Therefore, a risk minimization plan to prevent pregnancy must be observed.

Criteria for females of childbearing potential (FCBP)

This protocol defines a female of childbearing potential as a sexually mature female who: 1) has not undergone a hysterectomy or bilateral oophorectomy or 2) has not been naturally postmenopausal for at least 24 consecutive months (i.e., has had menses at any time in the preceding 24 consecutive months).

The investigator must ensure that:

- Females of childbearing potential comply with the conditions for pregnancy risk minimization, including confirmation that she has an adequate level of understanding
- Females NOT of childbearing potential acknowledge that she understands the hazards and necessary precautions associated with the use of metformin

Contraception

Females of childbearing potential (FCBP) enrolled in this protocol must agree to use a reliable forms of contraception simultaneously or to practice complete abstinence from heterosexual intercourse during the following time periods related to this study: 1) for at least 28 days before starting metformin; 2) throughout the entire duration of metformin treatment; 3) during dose interruptions; and 4) for at least 28 days after metformin discontinuation. FCBP must be referred to a qualified provider of contraceptive methods if needed. The following are examples of highly effective and additional effective methods of contraception:

Highly effective methods:

- oral contraceptive pills
- Intrauterine device (IUD)
- Hormonal (birth control pills, injections, implants)
- Tubal ligation
- Partner's vasectomy

Additional effective methods:

- Male condom
- Diaphragm
- Cervical Cap

The risk of venous thromboembolism continues for 4–6 weeks after discontinuing combined oral contraception. The efficacy of contraceptive steroids may be reduced during co-treatment with dexamethasone. Implants and levonorgestrel-releasing intrauterine systems are associated with an increased risk of infection at the time of insertion and irregular vaginal bleeding. Prophylactic antibiotics should be considered particularly in patients with neutropenia.

Pregnancy testing

Medically supervised pregnancy tests with a minimum sensitivity of 50 mIU/mL must be performed for females of childbearing potential, including females of childbearing potential who commit to complete abstinence, as outlined below.

Before starting metformin

Female Patients:

FCBP must have one pregnancy tests (sensitivity of at least 50 mIU/mL) prior to starting metformin.

During study participation and for 28 days following metformin discontinuation

Female Patients:

At each visit, the Investigator must confirm with the FCBP that she is continuing to use a reliable method of birth control at each visit during the time that birth control is required. If pregnancy or a positive pregnancy test does occur in a study patient, metformin must be immediately discontinued. Pregnancy testing and counseling must be

performed if a patient misses her period or if her pregnancy test or her menstrual bleeding is abnormal. Metformin treatment must be temporarily discontinued during this evaluation.

APPENDIX C

H-39773 Head and Neck Cancer Study Medicine Intake Calendar

Patient Name: _____

Instructions to Participant:

Use this calendar as a reminder to take your study medication every day. Record the number of pills/tablets that you take each day. Take the pills at about the same time every day.

Bring this calendar and your pills/tablets with you to each study visit.

Month: _____		Year: _____											
Sunday		Monday		Tuesday		Wednesday		Thursday		Friday		Saturday	
Sunday		Monday		Tuesday		Wednesday		Thursday		Friday		Saturday	

APPENDIX B**Blood glucose monitoring form**

Patient Name: _____

Instructions to Participant:

If your blood glucose is high, your doctor will ask you to monitor your glucose at home each day. Your doctor will give you the test you will need to do this.

You will do this for one week, two times a day.

Each day, write the date, and write your blood glucose value from each test on the form below. Bring this form back to your doctor or the research staff at your next visit.

DATE COLLECTED: _____ (MM/DD/YYYY)

Day of the week, Date	AM value	PM value
Monday, _____	value (mg/dl)	value (mg/dl)
Tuesday, _____	value (mg/dl)	value (mg/dl)
Wednesday, _____	value (mg/dl)	value (mg/dl)
Thursday, _____	value (mg/dl)	value (mg/dl)
Friday, _____	value (mg/dl)	value (mg/dl)
Saturday, _____	value (mg/dl)	value (mg/dl)
Sunday, _____	value (mg/dl)	value (mg/dl)

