7.2.1 Hypoglycemia: Although the risk of hypoglycemia in euglycemic patients receiving metformin is very low, patients in this trial might have a low caloric intake due to complications of treatment, and will undergo weekly blood glucose monitoring.

If based on these lab values or associated symptoms, the treating physician diagnoses hypoglycemia (Grade 1 or greater), study drug treatment will be halted, while concurrent chemoradiation will continue. Once blood glucose normalizes, metformin will be restarted and the dose should be decreased to the next available lower dose (see table below) with daily monitoring of blood glucose. Patients will

be provided equipment and supplies for twice daily blood glucose checks, along with a form used to record values.

Instructions for Metformin Dose Reductions due to Adverse Events	
Starting Dose (mg PO BID)	Reduced Dose (mg PO BID)
1500 mg	1350 mg
1350 mg	1000 mg
1000 mg	850 mg
850 mg	500 mg
500 mg	0 (off treatment)

If hypoglycemia resolves to < Grade 1 after 7 days, daily monitoring will be discontinued and the patient will resume the previous dose. All dose de-escalation and re-escalation will be recorded in source documentation. If **hypoglycemia** symptoms persist **for more than 7 days**, the study drug will be stopped and this will be considered a DLT.

722 Gastrointestinal toxicity: In the event of grade 2-4 gastrointestinal toxicity (typically involving flatulence or diarrhea), patients will be supported with loperamide, at dosing schedules recommended in the package insert. Gastrointestinal side effects typically subside within 4-6 weeks of initiating metformin treatment.

Efforts should be made to maintain the dose as close to the planned total daily treatment dose as much as possible. Before dose-reducing, alterations to the daily intake schedule of metformin should be taken to reduce gastrointestinal symptoms, including taking metformin with food rather than before meals.

If alterations in intake schedule are insufficient in reducing gastrointestinal toxicity to \leq grade 1, the metformin dose should be decreased to the next available lower dose for 1 week with loperamide support until symptoms subside.

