9.2 Study Calendar

	Pre-study	wk -2 (d3+/-2d)	wk 1 (d3+/-2d)	wk 2 (d3+/-2d)	wk 3 (d3+/-2d)	wk 4 (d3+/-2d)	wk 5 (d3+/-2d)	wk 6 (d3+/-2d)	wk 7 (d3+/-2d)	30 days post radiation completion	Post-study (wk17+/-2wk)	Post-study (yr1 Q3mos)	Post-study (yr2 Q4mos)
Metformin tx		<-----BID metformin----->											
Chemo-radiation tx			<-----XRT (Daily); chemotherapy (weekly)----->										
Collected information (ONCORE)													
Metformin pill diary/compliance form		x	x	x	x	x	x	x	x				
Eligibility checklist	x												
Informed consent	x												
T, N, M staging	x												
Demographics	x												
Physical Exam	x	x	x	x	x	x	x	x	x		x	x	x
Medical history	x												
Vital signs	x										x	x	x
Weight	x	x	x	x	x	x	x	x	x		x	x	x
Performance status	x	x	x	x	x	x	x	x	x		x	x	x
Adverse event evaluation		x	x	x	x	x	x	x	x	x	x		
CMP	x												
CBC, BMP	x	x	x	x	x	x	x	x	x		x	x	x
Glucose monitoring (if applicable) (A)		x	x	x	x	x	x	x	x				
Disease response/radiologic evaluation											x	x	x
Pregnancy test	x (B)												
Imaging (C)	x										x	x	x
Laryngopharyngoscopy											x	x	x
pre-study items to be collected within 30 days of initiation of metformin treatment													
Pill diary/compliant may be discussed or completed via telephone.													
A: patients with hypoglycemia (<=60mg/dl) will receive instructions and supplies for BID glucose monitoring and recording													
B: Serum or urine pregnancy test (women of childbearing potential).													
C: Required within 8-12 weeks prior to registration, at end of radiation treatment, and at regular intervals following treatment completion.													
D= day, Wk= week, Mos= months, Yr= year; d3+/-2d= to be completed on day 3 of any given week, +/- 2days													

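### The patient glucose form says home monitoring is for high blood glucose, but the protocol starts it only for hypoglycemia

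*Combined protocol and SAP*

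**What the plan says.** The patient form opens with "If your blood glucose is high, your doctor will ask you to monitor your glucose at home each day" and adds "You will do this for one week, two times a day". It has a morning and an evening box for each day of one week, and asks the patient to bring it back at the next visit. It does not mention low glucose.

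Section 7.2.1 (Hypoglycemia) works in the other direction. If, from laboratory values or symptoms, "the treating physician diagnoses hypoglycemia (Grade 1 or greater), study drug treatment will be halted, while concurrent chemoradiation will continue". When glucose is back to normal, metformin is resumed one step down the reduction table and glucose is then checked every day. Those affected are to "be provided equipment and supplies for twice daily blood glucose checks, along with a form used to record values". The rule for ending this is "If hypoglycemia resolves to < Grade 1 after 7 days, daily monitoring will be discontinued and the patient will resume the previous dose". Symptoms that last beyond 7 days stop the drug and count as a dose-limiting toxicity (DLT).

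Note A of the Study Calendar says that "patients with hypoglycemia (<=60mg/dl) will receive instructions and supplies for BID glucose monitoring and recording". Section 11 also ties daily monitoring to a diagnosis of hypoglycemia, and ends it after a week free of hypoglycemia.

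**The concern.** The form is the only written glucose instruction to patients in the document, and it states the reverse of the rule it serves. The patients who receive it have been diagnosed with hypoglycemia, have had metformin halted, and are restarting at a reduced dose. The protocol's stated reason for watching glucose is that chemoradiation may leave patients eating little. A patient in that position should not be told in writing that the problem is high glucose. The form also covers the 7 days after which section 7.2.1 allows monitoring to stop and the previous dose to resume, so it is in use when a clear shared understanding matters most.

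**Working it through.** No arithmetic applies to the contradiction itself. The check is a side-by-side reading.

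| Place | Reason for extra monitoring | Schedule |
|---|---|---|
| Patient form (second Appendix B) | Glucose is high | Twice a day, one week |
| Section 7.2.1 | Hypoglycemia, Grade 1 or greater, diagnosed by the physician | Daily monitoring with supplies for twice-daily checks; reviewed at 7 days |
| Study Calendar, note A | Hypoglycemia, 60 mg/dl or below | Twice a day |
| Section 11 | Hypoglycemia, no grade or value given | Daily; ends after 1 week without hypoglycemia |

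**Is it the same form?** Section 7.2.1 promises a recording form but cites no appendix. The form allows 7 days × 2 readings = 14 values, which fits twice-daily checks over the 7-day window. There is no other glucose form. The label Appendix B is also used for the pregnancy guidelines, so no cross-reference puts the reader right. The identification is an inference, but purpose, frequency and duration all agree.

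**Could the form serve some other rule, for high glucose?** The only high-glucose limit in the document is the eligibility exclusion in section 4.0, item s (glucose of 126 mg/dl or more, or hemoglobin A1c of 6.0% or more). That applies before registration. Sections 7 and 11 and the calendar contain no on-treatment action for high glucose. The form therefore has no such rule to serve.

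**Do the two low-glucose triggers agree?** Section 7.2.1 uses a physician's diagnosis by grade, which may rest on symptoms. Note A gives a value. The protocol grades events by CTCAE v4.0 but does not reproduce the cut-offs, so the documents alone do not show whether the two triggers coincide or differ.

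**How many patients?** The documents give no incidence. Sections 7.2.1 and 11 describe the risk as very low, so the number may be small or zero. It cannot be computed.

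**The case against.** The best case for leaving this alone is that the form does little beyond collecting numbers. It gives no threshold and no self-treatment advice, and a wrong opening sentence does not change a meter reading. The patient will already have had hypoglycemia diagnosed and the drug halted, and note A says instructions are given with the supplies. Weekly visits and weekly laboratory tests continue regardless. Patients with diabetes are excluded, so they should hold no other prescribed glucose-lowering drug to take in error. All of this stands and limits the size of the point. It does not remove the contradiction: a written safety instruction should not depend on staff saying the opposite.

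A reader might go further in three ways that the documents do not support.

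- *That the wording changes DLT counts and so the dose decisions.* Section 7.2.1 makes the DLT depend on symptoms lasting more than 7 days. Section 13.1 makes it depend on hypoglycemia requiring dose reduction, and under section 7.2.1 that reduction comes at restart, when monitoring begins. Neither turns on the form's opening sentence. Nor does one DLT in the first 3 patients necessarily change the action. The dated note in section 6.1 forgoes escalation to Dose level 2, and section 13.2 keeps accruing at the lowest level unless it is eliminated. If 850 mg is that lowest level, 0, 1 or 2 DLTs in 3 all mean continuing there. (A footnote in section 13.2 still describes the study as having escalated, so this relies on the note in section 6.1.)
- *That patients will respond to readings in the wrong direction.* This is possible but only inferred. What else patients are told cannot be judged from the text available.
- *That the trigger is set at three conflicting levels.* What is shown is one reversal, high against low. A conflict between note A and section 7.2.1 is not established.

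**Conclusion.** The contradiction is real and stands in current text. The form gives high glucose as the reason for home monitoring; the protocol gives hypoglycemia in all three places where it starts such monitoring, and has no on-treatment rule for high glucose. The consequence is limited to a misleading written instruction for the few patients expected to be placed on home monitoring. No endpoint, sample size, error rate or dose-decision boundary changes. It should be handled as a minor patient-safety document correction. The conclusion assumes that this is the form promised in section 7.2.1, and that any separate verbal or written instructions do not replace it; the second assumption cannot be checked from the documents.

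**What to change.** Reconcile the form with section 7.2.1, note A of the Study Calendar and section 11, so that it names the same condition as the protocol. At the same time, have the investigators confirm whether the trigger wording in section 7.2.1 and in note A is meant to be the same, and if so use one wording in both places. This review proposes no threshold. It would also help to give the form its own appendix letter and cite it in section 7.2.1. The cost is one line on a form, a consistency edit in the protocol, and whatever ethics-board submission is needed for a revised patient document (an assumption; the protocol does not describe that step). No analysis needs to be redone. The corrected form should replace the current one before more copies are issued.
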